9.6.3 Laboratory Test Results

Laboratory test results will be graded for severity using the NCI-CTCAE version 5.0 and will be summarized for each treatment arm using descriptive statistics for baseline values and changes from baseline values by cycle (per table 2-1 from protocol), and a summary of subject incidence of grade 3 and 4 laboratory abnormalities.

For the summary of changes from baseline values, subjects without a baseline and/or post-baseline value will be excluded; values from unscheduled assessments will not be included. Laboratory results from samples taken > 30 days after the last administration of protocol therapy will be excluded from all laboratory summaries.

Shifts in laboratory toxicity grades to outside the normal range will be evaluated for laboratory parameters by assessing the maximum increase and/or decrease observed

during the course of study treatment relative to the baseline toxicity grade. The following selected laboratory parameters may be considered in this analysis.

- (1) hematology analytes in decreasing direction: Hemoglobin, Lymphocyte, Absolute Neutrophil Count (ANC), Platelet, White Blood Cell (WBC);
- (2) chemistry analytes in increasing direction: Alanine Aminotransferase (ALT), Aspartate Aminotransferase (AST), Total Bilirubin, Corrected Calcium, Serum Creatinine, Potassium, Sodium, Magnesium, Uric Acid;
- (3) chemistry analytes in decreasing direction: Albumin, Corrected Calcium, Potassium, Magnesium, Phosphorus, Sodium.

The subject incidence of Grade 3 and 4 hematological laboratory abnormalities and the subject incidence of Grade 3 and 4 nonhematological toxicities (including liver function test (LFT), creatinine) will be provided by treatment arm in the same table.

The summary table for ALT, AST, Total Bilirubin, and the potential Hy's Law cases will also be considered.

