## 2.2 Schedule of Activities

**Table 2-1. Schedule of Activities**

PROCEDURE	Screening a (up to 28 days before random)	Treatment Period Cycles 1 to 12							Safety FU (30 [+3] days after last dose)	LTFU b (every 28 ± 7 days)	Notes
		Day 1	2	8	9	15	16	22			
GENERAL AND SAFETY ASSESSMENTS											
Informed consent	X										
Inclusion and exclusion criteria	X										
Demographics	X										
Medical history	X										Including multiple myeloma history
Substance use	X										Tobacco only
Complete physical examination	X							X			
Physical measurements	Height	X									
	BSA	X	(X)								BSA should be calculated during screening per Mosteller formula and utilized to calculate required study drug doses. BSA should be recalculated if weight changes by more than 20% (gain or loss) from weight used at the most recent BSA calculation.
	Weight	X	X								
12-lead ECG with QTc interval		X		(X)							Screening and as clinically indicated.
	cycle 1			X							To be performed at the end of carfilzomib infusion
	cycle 2		X								
Vital signs (once-weekly arm)	X	X	X	X	X			X			Checked prior to administration of carfilzomib in all cycles. In cycles 1 and 6, an additional blood pressure measurement post-carfilzomib infusion will be collected (within 30 minutes of the end of infusion).
Vital signs (twice-weekly arm)	X	X	X	X	X	X	X				
ECOG performance status	X							X			
Echocardiogram	X	(X)							X		During treatment every 6 months (± 2 weeks) from C1D1 until SFU and additionally as clinically indicated. An ECHO must be performed within 72 hours of the onset of a suspected cardiac failure event.

Page 1 of 8

Footnotes are defined on the last page of the table.

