**Table 2-1. Schedule of Activities**

PROCEDURE	Scree ning a (up to 28 days before rand)	Treatment Period Cycles 1 to 12							Safety FU (30 [+3] days after last dose)	LTFU b (every 28 ± 7 days)	Notes
		Day 1	2	8	9	15	16	22			
Survival										(X)	Subjects who terminate early from study treatment (less than 12 complete cycles) will be followed every 28 ± 7 days after safety follow-up visit until 12 months after randomization, death, loss to follow-up or withdrawal of full consent, whichever comes first.
Subsequent antimyeloma therapies										(X)	All subjects who have ended study treatment without a confirmed PD will be followed every 28 ± 7 days until 12 months after randomization, first subsequent antimyeloma, death, loss to follow-up, withdrawal of full consent, or confirmed PD, whichever comes first.
Adverse events/serious adverse events c		Continuous									
Concomitant therapies review		Continuous									
LABORATORY ASSESSMENTS											
Pregnancy test (FCBP only)	Serum	X						X		At screening: 10 to 14 days prior to C1D1	
	Urine or serum cycle 1 (predose)		X	X		X		X		Within 24 hours prior to dose of lenalidomide.	
	Urine or serum cycle 2 to 12 (predose; regular menses)		X								
	Urine or serum cycle 2 to 12 (irregular menses)		X			X					
Hematology		X	X						X		Hematology and chemistry samples from screening may be used for C1D1 if taken within 3 days prior to C1D1. Hematology and chemistry samples taken within 48 hours of D1 of subsequent cycles may be used for treatment decisions. Laboratory results must be evaluated for potential dose modification assessment prior to dosing.
Chemistry		X	X						X		

Footnotes are defined on the last page of the table.

Page 2 of 8

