#### **9.1.3 Safety Follow-up**

Upon permanent discontinuation from the study treatment for any reason (including subjects who complete 12 cycles of treatment), a safety follow-up visit will be performed approximately 30 (+3) days after the last dose of all study drug(s) unless the subject is lost to follow-up, has withdrawn full consent, or has died. Subjects who discontinue treatment due to confirmed PD are also to complete the safety follow-up visit.

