##### **9.2.3.1      Adverse Events**

###### **9.2.3.1.1      Time Period and Frequency for Collecting and Reporting Safety Event Information**

###### **9.2.3.1.1.1      Adverse Events**

The adverse event grading scale to be used for this study will be the Common Terminology Criteria for Adverse Events (CTCAE) and is described in Section 12.4.

The investigator is responsible for ensuring that all adverse events observed by the investigator or reported by the subject that occur after signing of the ICF through 30 (+3) days after the last dose of all study drug(s) are reported using the Event eCRF.

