3.1 Study Design

This is a phase 3, multicenter, open-label, randomized study in subjects with RRMM who have received 1 to 3 prior therapies.

Subjects will be randomized in a 1:1 ratio to 1 of 2 arms:

Arm 1: KRd using carfilzomib 56 mg/m² QW

Arm 2: KRd using carfilzomib 27 mg/m² BIW

Randomization will be performed using an interactive voice/web response system (IxRS) and subjects will be stratified based on the following criteria: original International Staging System (ISS) stage at study entry (stage 1 or 2 vs stage 3); prior lenalidomide treatment (yes vs no), prior proteasome inhibitor (PI) treatment (yes vs no), prior anti-CD38 exposure (yes vs no).

Subjects will receive the study drug(s) determined by randomization for a maximum of 12 cycles. No crossover between the treatment arms is allowed. After completion or discontinuation of all study drug(s), subjects will have a safety follow-up visit 30 (+3) days after the last dose of all study drug(s).

All subjects will be assessed for multiple myeloma disease response and disease progression by investigator and a blinded Independent Review Committee (IRC) according to the International Myeloma Working Group-Uniform Response Criteria (IMWG-URC) ([Kumar et al, 2016](#); [Rajkumar et al, 2011](#); [Durie et al, 2006](#)) using central laboratory test results every 28 ± 7 days from cycle 1 day 1 through the end of cycle 12 or disease progression until death, loss to follow-up, withdrawal of full consent, or first subsequent antimyeloma treatment (whichever occurs first), regardless of treatment cycle duration, dose delays or treatment discontinuation. The disease assessment schedule is independent of treatment schedules.

Following the safety follow-up visit, subjects who do not have confirmed progressive disease (PD) before 12 months from randomization are required to continue follow-up every 28 ± 7 days for survival, disease response assessments and report new antimyeloma treatment until 12 months after randomization, first subsequent antimyeloma treatment, death, loss to follow-up, withdrawal of full consent, or confirmed PD, whichever occurs first.

Following the safety follow up visit, all subjects with confirmed PD before 12 months from randomization will be followed for survival every 28 ± 7 days until 12 months after

randomization, death, loss to follow-up, or withdrawal of full consent, whichever comes first.

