9.6.4 Vital Signs

Vital sign results (systolic/diastolic blood pressure, heart rate, respiratory rate, and temperature) will be summarized using descriptive statistics for baseline values and changes from baseline by cycle for each treatment arm.

For the summary of changes from baseline, subjects without a baseline and/or post-baseline value will be excluded; values from unscheduled assessments will not be included. Vital sign results taken > 30 days after the last administration of protocol therapy will be excluded from all vital sign summaries.

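### The 30-day cut-off in SAP 9.6.3 and 9.6.4 leaves out on-time safety follow-up laboratory and vital-sign results from days 31 to 33

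*SAP*

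**What the plan says.** **Cut-off.** SAP 9.6.3 on laboratory data: "Laboratory results from samples taken > 30 days after the last administration of protocol therapy will be excluded from all laboratory summaries". SAP 9.6.4 on vital signs: "Vital sign results taken > 30 days after the last administration of protocol therapy will be excluded from all vital sign summaries".

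**Visit.** Protocol 9.1.3 says that on permanent discontinuation, including completion of 12 cycles, "a safety follow-up visit will be performed approximately 30 (+3) days after the last dose of all study drug(s"). SAP 3.1 and the column header of Protocol Table 2-1 give the same 30 (+3) day timing. The stated tolerance is on the late side only.

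**Samples.** Table 2-1 schedules hematology and chemistry at screening, on day 1 of each cycle and at safety follow-up.

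**Summaries.** SAP 9.6.3 asks first to describe the baseline, then to give "changes from baseline values by cycle (per table 2-1 from protocol), and a summary of subject incidence of grade 3 and 4 laboratory abnormalities". In the change-from-baseline summary it leaves out unscheduled values and any subject with no baseline or no post-baseline value.

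**Neighbouring windows.** SAP section 5 ends the treatment-emergent adverse event (TEAE) period 30 days, inclusive, after the last dose of any study drug. Protocol 9.2.3.1.1.1 collects adverse events "that occur after signing of the ICF through 30 (+3) days after the last dose of all study drug(s) are reported using the Event eCRF".

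**The concern.** The SAP cut-off falls at the first day of the visit window, so a site can follow the protocol exactly and still have its results left out of the tables. The protocol asks for a hematology and chemistry sample at this visit, and it is the only scheduled one after the final cycle's doses. Safety and tolerability is a stated secondary objective, assessed partly through laboratory tests and vital signs (SAP 2.1 and 9.6.1). Inclusion would turn on whether the appointment fell on day 30 or a day or two later, which has no bearing on the subject's safety.

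**Working it through.** The plan gives no figure to reproduce. The check applies the SAP rule to each day of the permitted window. It assumes that the last administration of protocol therapy (SAP 9.6.3, 9.6.4) and the last dose of all study drugs (Protocol 9.1.3) are the same date.

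**Step 1: permitted days.** 30 (+3) gives days 30, 31, 32 and 33.

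**Step 2: apply the rule (exclude if day > 30).**

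| Day after last dose | > 30? | In the summaries? |
|---|---|---|
| 30 | no | yes |
| 31 | yes | no |
| 32 | yes | no |
| 33 | yes | no |

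Three of the four permitted days fall outside the cut-off. With the rule set to > 33, all four are kept.

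**Step 3: share of results lost.** Share lost = (on-time visits on days 31 to 33) / (all on-time visits). The documents do not give the distribution of visit days. The share is 0% if every visit is on day 30 and 100% if none is.

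**Step 4: which tables are affected.**

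- *Grade 3 and 4 laboratory incidence.* This summary is not limited to a cycle, and the exclusion covers all laboratory summaries. A grade 3 or 4 value first seen on days 31 to 33 is not counted.
- *Change from baseline.* The summary is by cycle, with a reference to Table 2-1, which has a safety follow-up column. If that column is summarised, its results from days 31 to 33 are lost. Take a hypothetical subject whose last dose of any study drug is on cycle 1 day 15. Permitted visit days are study days 15 + 30 = 45 to 15 + 33 = 48. Under SAP section 5, baseline is the latest value on or before day 1, and there is no cycle 2 day 1 sample, so safety follow-up is the only scheduled post-baseline hematology and chemistry sample. A visit on study day 47 is 47 − 15 = 32 days after the last dose and is excluded. With unscheduled values barred, the subject has no usable post-baseline value and leaves the table.
- *Shift tables.* SAP 9.6.3 bases these on the extreme values seen while on study treatment, so they may be little affected.
- *Vital signs.* These are taken at every carfilzomib dosing visit, so less depends on the follow-up visit. In the text copy of Table 2-1 used here, the once-weekly row appears to carry a safety follow-up mark. The twice-weekly row shows seven marks, which match screening plus six dosing days. A follow-up measurement in that arm cannot be confirmed from this copy.

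**Step 5: look for a rescuing clause.** The SAP contains no visit-window rule or exception that restores these results. Elsewhere it does allow for windows: the 63-day rule for missed disease assessments (Table 5-1) is 2 × 28 + 7 days. Safety follow-up data for convenience, QLQ-C30 and CTSQ (SAP 9.5.2) carry no 30-day limit.

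**The case against.** The strongest reply is that 30 days is a deliberate on-treatment window. The SAP uses it for TEAEs (section 5), for classifying deaths (9.6.2) and for concomitant medications (9.6.9), and Protocol 7.8.2 collects concomitant therapies for 30 days. Laboratory and vital-sign summaries are by cycle, and safety follow-up is not a cycle; where the SAP wants that visit it usually names it. There are also other routes of capture. The bar on unscheduled values is written for change from baseline, so such values within 30 days can still enter grade 3 and 4 incidence. Local results of grade 3 or higher go on the eCRF (Protocol 12.2), and laboratory changes needing treatment or an adjustment of therapy are adverse events (Protocol 9.2.4).

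Much of this stands, and it limits the size of the point. It does not remove the mismatch. The SAP gives no rationale for excluding an on-time visit, it refers to Table 2-1 for the laboratory summaries, and the protocol's adverse event collection runs to 30 (+3) days. The adverse event route does not fully compensate either, because an event starting on days 31 to 33 is not a TEAE.

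Several stronger readings are tempting but unsupported:

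- *Three quarters of the results are lost.* Three of four days is a count of days. It becomes a share of visits only if visits are spread evenly, which the documents do not say.
- *Only visits on exactly day 30 survive.* Protocol 9.1.3 says approximately, so a slightly early visit is conceivable and would be kept.
- *The data are thrown away.* They are collected and retained; only the summaries omit them.
- *The Hy's Law table is compromised.* SAP 9.6.3 says only that this table will be considered.
- *The arms are biased against each other.* The cut-off is the same in both, and nothing in the documents shows a differential effect.

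**Conclusion.** The mismatch is real and follows from the text alone: laboratory results from a compliant safety follow-up visit on days 31, 32 or 33 are left out of all laboratory summaries, and any vital signs taken then are left out of theirs. The consequence is modest. It is confined to descriptive safety tables; the primary and key secondary analyses are unaffected. Grade 3 and 4 laboratory incidence is the clearest place of loss. For subjects who stop in cycle 1, the change-from-baseline loss depends on safety follow-up being summarised per Table 2-1. The vital-sign effect is smaller and unconfirmed in the twice-weekly arm. The number of results lost cannot be estimated from the documents.

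The conclusion rests on two readings: that both windows count from the same last dose, and that the third mark in the hematology and chemistry rows of Table 2-1 belongs to safety follow-up, as the columns in the available copy are shifted.

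**What to change.** In SAP 9.6.3 and 9.6.4, state that results from the scheduled safety follow-up visit within its 30 (+3) day window are included in the summaries, or change the cut-off from > 30 to > 33 days. In 9.6.3, also say whether safety follow-up is a time point in the change-from-baseline table.

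Consider extending the TEAE window in SAP section 5, now 30 days inclusive, to match the protocol's 30 (+3) day adverse event collection period. If only the laboratory and vital-sign rule changes, an abnormality on days 31 to 33 would count in the laboratory table while an adverse event starting that day would not be a TEAE. That is a small downside, and it is avoided by changing both or by explaining the difference in a footnote.

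The cost is a line or two of SAP text and a small programming change. No new data are needed.

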9.6.4 Vital Signs

Vital sign results (systolic/diastolic blood pressure, heart rate, respiratory rate, and temperature) will be summarized using descriptive statistics for baseline values and changes from baseline by cycle for each treatment arm.

For the summary of changes from baseline, subjects without a baseline and/or post-baseline value will be excluded; values from unscheduled assessments will not be included. Vital sign results taken > 30 days after the last administration of protocol therapy will be excluded from all vital sign summaries.

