Secondary	
PFS over the duration of the study: Kaplan-Meier (KM) estimates for PFS distribution by treatment and PFS rates and CI at 6 and 12 months, stratified Cox proportional hazards (PH) model for HR and CI estimate. The synthesis approach will be used to show that once-weekly KRd 56 mg/m^2 preserves at least 50% of twice-weekly KRd 27 mg/m^2 effect vs Rd.
 
Patient-reported convenience after cycle 4 of treatment: Cochran-Mantel-Haenszel method will be used to evaluate the treatment effect (OR) for whether carfilzomib dosing is reported as convenient or inconvenient; a logistic regression model including the randomization stratification factors and treatment group will be considered for sensitivity analysis
 
Time to response: mean, SD, median, minimum and maximum among responders.
 
Duration of response (DOR): KM method among responders.
 
Time to progression (TTP): KM method and stratified Cox PH model.
 
OS over the duration of the study: KM estimates for OS distribution by treatment and OS rates and CI at 6 and 12 months, stratified Cox PH model for HR and CI estimate.
 
MRD[-]CR: proportion of MRD[-]CR will be reported with CI calculated using Clopper-Pearson method.
 
MRD[-] status at 12 months from randomization: proportion of MRD[-] will be reported with CI calculated using Clopper-Pearson method.
 
Physical functioning and role functioning (EORTC QLQ-C30) over time: repeated measures analysis of covariance adjusting for the baseline covariates. A restricted maximum likelihood-based mixed model for repeated measures (MMRM) will be considered as sensitivity analysis.
 
Patient-reported treatment satisfaction (CTSQ) after cycle 4 of treatment: analysis of covariance at the corresponding fixed time point.

Exploratory	Will be described in the statistical analysis plan finalized before database lock.

Safety analyses will be based on the safety population (defined as all randomized subjects who have received at least 1 dose of any study treatment [carfilzomib, lenalidomide, or dexamethasone]). The number and percentage of subjects experiencing 1 or more adverse events will be summarized by treatment group, relationship to study treatment, and severity. Changes from baseline and shift in toxicity grade in safety laboratory test results, left ventricular ejection fraction and vital signs will

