#### **Additional Vital Sign Measurements**

In cycles 1 and 6, an additional blood pressure measurement post-carfilzomib infusion will be collected (within 30 minutes of the end of infusion).

Record all measurements on the vital signs eCRF. For blood pressure, record the average blood pressure.

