#### **10.3.2.3.3 Vital Signs**

The vital signs and their change from baseline will be summarized by cycle.

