9.1 General Considerations

Where applicable, descriptive statistics will be provided. For continuous variables, the number of subjects with non-missing data (n), mean, standard deviation (STD), median, minimum, and maximum will be presented. For categorical variables, the frequency (n) and percentage will be summarized in each category. The denominator for percentages is the number of subjects in the analysis set of interest for the summary. The binomial proportions and the corresponding 95% confidence intervals (CIs) will be based on the exact distribution methods (Clopper-Pearson interval) and the treatment comparison will be based on Cochran-Mantel-Haenszel (CMH) method. Time to event endpoints will be estimated using the Kaplan-Meier (KM) method and will be summarized with the number of subjects with events or censored, and censoring reasons, KM quartiles (when estimable) and corresponding two-sided 95% CIs, KM proportions at select time points, inferential comparison between treatment arms with associated p-values, hazard ratios from stratified Cox proportional hazard (PH) model, and KM curves.

The analyses of efficacy and safety endpoints will be based on the analysis sets defined in [Section 6](#). The primary (final) analyses of the efficacy endpoints and Patient-report outcomes will use the ITT population, while the Per Protocol Set will be used for sensitivity analyses, if applicable. The analyses of the safety endpoint will be based on the safety population.

The primary analysis of ORR and PFS will be based on IRC assessed outcomes. The synthesis approach will be used to show that KRd 56 mg/m² QW preserves at least 60% of KRd 27 mg/m² BIW effect vs Rd in terms of ORR and 50% in terms of PFS. The null hypotheses for the primary and key secondary objectives (ORR, PFS, and convenience after cycle 4 of treatment) will be tested using a fixed sequence hierarchical testing procedure to control the family-wise type I error rate at 1-sided 0.025 level. The testing is ordered as follows: non-inferiority of ORR, non-inferiority of PFS, and superiority of patient-reported convenience after cycle 4 of treatment. Starting with the hypothesis of ORR, if any null hypothesis in the sequence is rejected, then the subsequent hypothesis

will be tested. Otherwise, if any hypothesis failed to be rejected, then the subsequent hypotheses will not be tested. For all other endpoints, the significance testing, if performed, will be considered descriptive.

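### SAP 9.6.4 has no per-subject count of measured blood-pressure peaks, no rule for the mandated post-infusion readings, and no vital-sign grade shift, which the synopsis announces

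*SAP*

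**What the plan says.** **Collection.** Protocol Table 2-1 requires vital signs to be "Checked prior to administration of carfilzomib in all cycles". Protocol 9.2.3.2 adds: "In cycles 1 and 6, an additional blood pressure measurement post-carfilzomib infusion will be collected (within 30 minutes of the end of infusion". Each recorded pressure is already the average of at least three measurements taken minutes apart.

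**Analysis in the SAP.** SAP 9.6.4 says that vital sign results "will be summarized using descriptive statistics for baseline values and changes from baseline by cycle for each treatment arm". For the change summaries, "values from unscheduled assessments will not be included". SAP 9.1 defines the statistics: "For continuous variables, the number of subjects with non-missing data (n), mean, standard deviation (STD), median, minimum, and maximum will be presented". Section 9.6.4 does not mention the post-infusion readings. It has no grade shift, worst-value table or threshold count.

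**Analysis in the protocol.** The synopsis, under Statistical Considerations, reads: "Changes from baseline and shift in toxicity grade in safety laboratory test results, left ventricular ejection fraction and vital signs will"; the sentence goes on to say that these are summarized descriptively. The body text in 10.3.2.3.3 is shorter: "The vital signs and their change from baseline will be summarized by cycle". SAP section 10, which lists changes from the protocol, names only the restricted mean survival time, the retention rate and the ORR margin.

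**The concern.** Protocol 3.3.3 names hypertension as a key risk of carfilzomib, alongside cardiac failure and acute renal failure. The trial is open-label (protocol 7.3). Under protocol Appendix 4, an abnormal vital sign becomes an adverse event when the investigator judges it clinically significant. Measured pressures are the one source on this risk that depends less on that judgment.

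The plan collects those pressures, including a set taken just after infusion, but summarizes them in a form that cannot say how many subjects in each arm reached a high value. Laboratory tests are treated differently: under SAP 9.6.3, "Shifts in laboratory toxicity grades to outside the normal range will be evaluated for laboratory parameters" by the largest on-treatment departure from the baseline grade.

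The arms also differ in infusions per cycle, dose per infusion and infusion time. How several readings become one by-cycle figure therefore matters for the comparison, and that rule is not written down.

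**Working it through.** The plan states no figure on this point, so the check is mainly a comparison of texts. A small illustration follows.

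**1. Grade shift, three texts side by side.**
- Synopsis: change from baseline and shift in toxicity grade, for laboratory tests, LVEF and vital signs.
- Protocol 10.3.2.3.3: vital signs and change from baseline by cycle; no shift.
- SAP 9.6.4: baseline values and change by cycle; no shift. SAP section 10 does not mention the matter.

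The SAP agrees with the body of the protocol and not with its synopsis. The same synopsis sentence covers LVEF, and SAP 9.6.7 has no shift for that either.

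**2. What the by-cycle table can show.** It gives n, mean, standard deviation, median, minimum and maximum. The maximum shows the largest scheduled change per arm and cycle. That is one extreme value, with no number or percentage of subjects behind it and no unscheduled readings.

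**3. Readings per cycle.** The once-weekly arm has 3 infusions (days 1, 8, 15). The twice-weekly arm has 6 (days 1, 2, 8, 9, 15, 16). Pre-infusion readings per cycle are therefore 3 and 6. The text does not say whether the extra reading in cycles 1 and 6 follows every infusion or is taken once, so both are shown:
- after every infusion: 3 + 3 = 6 and 6 + 6 = 12 readings;
- once per cycle: 3 + 1 = 4 and 6 + 1 = 7 readings.

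Suppose, as one possible implementation, that all readings in a subject's cycle are averaged. A single rise of 40 mmHg (assumed) then adds:
- 40/6 = 6.7 mmHg once-weekly and 40/12 = 3.3 mmHg twice-weekly, or
- 40/4 = 10.0 mmHg and 40/7 = 5.7 mmHg.

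If one fixed reading represents the cycle, a rise on any other occasion adds nothing. The result depends on a rule that the SAP does not give, and under averaging the dilution differs by arm.

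**4. Why a cycle mean does not replace a count.** The documents give no rate of measured peaks. As a stand-in, take the grade 3 or higher hypertension event rates in protocol 3.3.3.1.2: 5.5% and 5.9% in A.R.R.O.W. (twice- and once-weekly) and 6.4% with KRd in ASPIRE. With about 230 subjects per arm:
- affected subjects = 230 × 0.055 = 12.7 to 230 × 0.064 = 14.7;
- shift of the arm mean = rate × rise, from 0.055 × 20 = 1.1 mmHg to 0.064 × 60 = 3.8 mmHg, if all of them rise by 20 to 60 mmHg (assumed) in the same cycle.

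Rises spread over several cycles would move each cycle's mean less. This shows only that a mean is insensitive to peaks in a minority. It does not estimate a difference between arms.

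**5. What the adverse event tables already cover.** SAP 9.6.2 tabulates reported events by preferred term and severity, with the worst grade per subject, grade 3 or higher, events leading to dose reduction or interruption, and events of interest. The SAP does not list which events are of interest.

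**The case against.** The case against is substantial, and much of it stands.

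- *A reader might infer that only means are reported.* SAP 9.1 rules this out: the median, minimum and maximum are shown as well.
- *A reader might infer that hypertension peaks vanish from the report.* They do not. The largest scheduled change is displayed, and reported hypertension is graded and counted in the adverse event tables. Regular DMC safety review adds a further safeguard.
- *A reader might infer that the SAP dropped a protocol analysis on its own.* The SAP follows protocol 10.3.2.3.3, and the synopsis refers readers to Section 10 for the full methods. The synopsis sentence can also be read so that the grade shift applies to laboratory tests alone, because the next sentence assigns CTCAE grading only to adverse events and laboratory results. The conflict lies first within the protocol.
- *A reader might infer that pre- and post-infusion readings will be pooled.* The SAP is silent, and silence is not a decision to pool.
- *A reader might expect the arms to differ.* The documents do not support assuming so. In A.R.R.O.W., hypertension of any grade was 21.8% once-weekly and 21.3% twice-weekly; grade 3 or higher was 5.9% and 5.5%.
- The exclusion of unscheduled values also applies to laboratory change summaries in SAP 9.6.3, so it is not peculiar to vital signs.
- A worst-value table has its own biases. Unscheduled readings depend on clinician concern, and more readings in the twice-weekly arm raise the chance of a high maximum.

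These points narrow the concern but leave a gap. No table counts subjects by measured peak, no rule covers the mandated post-infusion readings, and the texts on grade shift remain unreconciled. The biases of a worst-value table can be handled by showing it in two ways.

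**Conclusion.** The concern holds in a limited form. SAP 9.6.4 leaves three things open: a per-subject summary of the highest measured pressure, the handling of the post-infusion readings in cycles 1 and 6, and the vital-sign grade shift that the synopsis states and protocol 10.3.2.3.3 omits.

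The consequence is a missing check, not a demonstrated bias. The safety objective is descriptive and its endpoint, the incidence of treatment-emergent adverse events, is fully tabulated. The gain is a more objective companion to open-label event reporting on a named key risk. Its size cannot be computed, because the documents give no rate of measured peaks. The dilution figures rest on assumed rises of 20 to 60 mmHg, on event rates used as a stand-in and, in step 3, on averaging within a cycle. The textual findings depend on none of these. The change is worth making because it is cheap and matches what the SAP already does for laboratory tests.

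**What to change.** In SAP 9.6.4:

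1. Summarize pre-infusion and post-infusion blood pressure separately in cycles 1 and 6, and state which reading or visit enters the by-cycle summary.
2. Add a shift from baseline to the worst on-treatment value for systolic and diastolic pressure, as n (%) per arm. Use CTCAE grade, or levels the protocol already names (140/90 in Table 7-3, 160/100 in exclusion criterion 214), as reporting categories only. Show it once with all readings, including unscheduled ones, and once restricted to scheduled pre-infusion readings on days 1, 8 and 15, which both arms share.
3. Reconcile the synopsis, protocol 10.3.2.3.3 and SAP section 10. Either the grade shift for vital signs is planned, or its absence is declared with a reason. Settle LVEF at the same time, since the same synopsis sentence covers it.

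The cost is SAP wording and one or two tables from data already collected. The restricted version discards some twice-weekly readings, which is why both versions are needed. No treatment or dose-modification rule is touched.
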